### 1.2.4 Potential Toxicities of CNIs

Increased blood pressure (BP) and renal dysfunction are well known potential toxicities of CNIs that are dose-related, reversible, and generally responsive to dose reduction or temporary interruption of treatment [27].

Voclosporin has been studied in numerous disease states. In clinical studies of voclosporin in LN [9], a small proportion of voclosporin-treated subjects experienced an early drop of  $\geq 30\%$  in eGFR; however, that proportion then remained stable over time. None of these treatment-emergent adverse events (TEAEs) were classed as serious. The majority of TEAEs of

decreased GFR were classed as mild or moderate, and resulted in permanent discontinuation of study treatment in 1 (1.1%) placebo subject, 7 (7.9%) voclosporin low-dose (23.7 mg BID) subjects and 5 (5.7%) voclosporin high-dose (39.5 mg BID) subjects. There were more TEAEs of hypertension seen in the voclosporin-treated subjects compared to placebo; however, overall mean systolic and diastolic BP decreased in all groups, without statistically significant differences seen between groups. Overall, only 1 (1.1%) subject, in the voclosporin high-dose group, had a TEAE of hypertension that resulted in permanent discontinuation of study treatment.

There was also evidence of an increased incidence of TEAEs over placebo and with increased dose of voclosporin in the System Organ Classes of Infections and Infestations, Gastrointestinal Disorders, and Vascular Disorders.

## 2. RATIONALE

The rationale for the development of voclosporin and the range of dose is to introduce a novel CNI to the population of patients with FSGS, with meaningful efficacy while minimizing toxicities common to other CNIs. In clinical studies, a favorable efficacy/safety profile for voclosporin has been demonstrated in the prevention of renal transplant rejection and in Phase 2 studies in LN.

As evaluated in nonclinical and clinical studies (healthy volunteers, moderate to severe psoriasis, renal transplantation, and uveitis) voclosporin is well tolerated and exhibits adverse events (AEs) that are typical of other CNIs yet seen to a lesser extent than those seen historically with other CNIs.

The aim of the current study is to investigate whether voclosporin is able to reduce disease activity over a treatment period of 24 weeks. Subjects with histologic evidence of primary FSGS with proteinuria will be eligible to enter the study. Efficacy will be assessed by the ability of voclosporin to reduce the level of proteinuria (as measured by UPCR) while demonstrating an acceptable safety profile. The primary endpoint of this study will be complete or partial remission of proteinuria at 24 weeks.

### 2.1 Dose Rationale

This Phase 2 study is designed to initially evaluate the treatment benefit of voclosporin 23.7 mg BID in the first cohort of up to 10 subjects. The selection of this voclosporin dose for the first cohort (see [Section 7, Study Treatments](#)) was based on the previous experience with this drug in the Phase 2 LN study (AURA-LV). In AURA-LV, subjects were administered voclosporin 23.7 mg BID, voclosporin 39.5 mg BID, or matching placebo. Low-dose voclosporin was significantly superior to placebo in the proportion of subjects achieving complete renal response at Week 24 ( $p=0.045$ ). At Week 48, complete remission rates in both the low-dose (49.4%) and high-dose (39.8%) voclosporin groups demonstrated statistically significant superiority compared to the placebo (23.9%) group, ( $p<0.001$ ,  $p=0.026$ , respectively). There was no increase in efficacy with the higher dose and no significant differences between the two voclosporin groups in achievement of renal response.

This study is also designed to evaluate a further dose level of voclosporin, this dose may be higher or lower than the initial 23.7 mg BID dosing. When the first 5-6 subjects in Cohort 1 have completed 12 weeks of treatment with voclosporin, the top line efficacy and safety data will be analyzed to determine the dose level for Cohort 2. The maximum dose possible for Cohort 2 will be 39.5 mg (5 capsules) BID. If the higher dose is selected for Cohort 2, subjects still receiving treatment in Cohort 1 may have their dose increased to 39.5 mg after Week 8 if they have not demonstrated meaningful benefit from the 23.7 mg BID dose per Investigator judgement and following discussion with the Medical Monitor. Subjects enrolled after the dose decision will receive voclosporin at 39.5 mg BID and be considered part of Cohort 2.

To minimize safety concerns, a cautious dose-escalation design starting with a minimal dose of one capsule (7.9 mg) per day will be employed for all subjects (see [Section 7.1.2, Dosing Guidelines](#)).

The protocol contains provisions for management of dose (including rules for stopping treatment with study medication) based on safety concerns in particular, BP and renal function. The safety data from the use of voclosporin in LN demonstrates that these risks are dose-related, reversible, and can be managed by dose reduction and temporary interruption.

Furthermore, voclosporin will be administered as fixed doses without the use of therapeutic drug monitoring. Population PK analyses of voclosporin concentrations from the clinical development program (including healthy subjects, subjects with renal impairment, subjects with hepatic impairment, renal transplant, plaque psoriasis, and LN) demonstrated that weight did not have a significant effect on the PK of voclosporin [9].

### **3. STUDY OBJECTIVES**

#### **3.1 Primary Objective**

- To assess the efficacy of voclosporin in achieving complete or partial remission of proteinuria after 24 weeks of therapy in subjects with FSGS.

#### **3.2 Secondary Objective**

- To assess the safety and tolerability of voclosporin over 24 weeks in subjects with FSGS.

#### **3.3 Endpoints**

All primary and secondary endpoints will be assessed overall and for each individual cohort.

##### **3.3.1 Primary Endpoint**

Proportion of subjects with remission of proteinuria at Week 24 based on the following parameters:

- Complete remission: UPCR of  $<0.3$  mg/mg  
OR
- Partial remission: UPCR  $\geq 0.3$  mg/mg and  $<3.0$  mg/mg with  $>50\%$  reduction in UPCR from baseline

##### **3.3.2 Secondary Endpoints**

- Proportion of subjects with complete remission or partial remission of proteinuria at Weeks 8 and 12
- Proportion of subjects with complete remission of proteinuria at Weeks 8, 12, and 24
- Proportion of subjects with UPCR  $<0.5$  mg/mg at Weeks 8, 12, and 24
- Proportion of subjects with partial remission of proteinuria at Weeks 8, 12, and 24
- Time to first occurrence of complete or partial remission of proteinuria
- Time to first occurrence of complete remission of proteinuria
- Time to first occurrence of partial remission of proteinuria
- Time to first occurrence of 50% reduction in UPCR from baseline
- Duration of UPCR  $<0.3$  mg/mg

- Change from baseline in UPCR at each time point
- Proportion of subjects with a confirmed >30% decrease from baseline in eGFR (utilizing the Chronic Kidney Disease Epidemiology Collaboration (CKD-EPI) formula) at each time point
- Proportion of subjects with a confirmed >30% increase in eGFR from the final visit (Week 24 or last on-treatment visit, for subjects who discontinue prematurely) to the second Safety Follow-up visit (Visit 10)
- Change in UPCR from the final visit (Week 24 or last on-treatment visit, for subjects who discontinue prematurely) to the second Safety Follow-up visit (Visit 10)
- Change in eGFR from the final visit (Week 24 or last on-treatment visit, for subjects who discontinue prematurely) to the second Safety Follow-up visit (Visit 10)
- Change from baseline in serum creatinine, serum albumin, and eGFR at each time point
- Quality of life (QoL) assessments
  - Mean change in Patient Reported Outcome Measurement Information System (PROMIS) measures at Week 24
  - Change from baseline in Kidney Disease Quality of Life-Short Form (KDQOL-SF™) score at Week 24
- Safety and tolerability over 24 weeks
- Renal biopsy: descriptive analyses of changes in histopathology will be evaluated in post-treatment (24 weeks) renal biopsies in a subset of patients
- Change from baseline to Week 4 and 24 in the following biomarkers:
  - Urine nephrin
  - Urine synaptopodin
  - Serum TGF- $\beta$

## 4. INVESTIGATIONAL PLAN

### 4.1 Overall Study Design

This is a Phase 2, open-label, multicenter, prospective, 24-week, exploratory cohort study to assess the efficacy and safety of two dose levels of voclosporin in achieving complete or partial remission of proteinuria in subjects with biopsy-confirmed primary FSGS. Subjects who have provided a signed and dated informed consent will be screened into the study. Subjects will be assigned a unique subject number which will be used to identify them throughout the study. The duration of the screening period will be approximately 4 weeks to 10 weeks (allowing for visit windows (14±3 days) for each stability assessment) to ensure that subjects meet eligibility criteria, including renal disease stability assessments. If a subject has not had a renal biopsy within the 6-month (prior to screening) required timeframe for study eligibility, one may be performed to assess eligibility into the study, provided the subject has given consent and provided the results can be obtained and reviewed before baseline; biopsy results over 6 months prior to screening may be permitted following review with the Medical Monitor. Subjects who meet all of the inclusion criteria and none of the exclusion criteria will be eligible to receive treatment with voclosporin. Up to 10 subjects will be enrolled into Cohort 1, at a starting dose of 7.9 mg BID for Week 1, 15.8 mg BID for Week 2, and a target dose of 23.7 mg BID for Weeks 3 to 24. The first dose of study treatment should occur in the morning on Day 2, the day after dispensing. Subjects will be contacted by telephone at the end of Week 1 and Week 2 to be reminded to increase their dose as per [Section 7.1.2.1, Voclosporin Study Treatment](#).

Evaluable safety and tolerability from 12 weeks of treatment in the first 5-6 subjects from Cohort 1 are required in order to determine the dose level for Cohort 2. The dose selected may be higher or lower than 23.7 mg BID. The maximum dose possible for Cohort 2 will be 39.5 mg (5 capsules) BID. Dosing in this group will follow the same cautious approach as Cohort 1, with at a starting dose of 7.9 mg BID for Week 1, 15.8 mg BID for Week 2, 23.7 mg BID for Week 3 and a maximum dose of 39.5 mg BID for Weeks 4 to 24.

Doses and dose increments smaller than anticipated or an intermediate dose may be proposed for Cohort 2 based on the safety and tolerability results from the Cohort 1.

All subjects will return for assessment of efficacy and safety at Weeks 2, 4, 8, 12, 18, and 24. See [Schedule of Events](#), for detailed information regarding visits.

All subjects, completed or withdrawn from the study, will complete the End of Treatment/Early Termination assessments (Visit 8) at Week 24, or at the time of withdrawal, and should attend two Safety Follow-up visits at 1 and 2 weeks after completion of treatment (i.e., at Week 25 (Visit 9) and Week 26 (Visit 10)) (or 7 and 14 days, respectively, following withdrawal) to collect any new AEs and concomitant medications. At the follow-up visit, UPCR and eGFR

will be assessed as well. For subject withdrawal procedures and criteria, see [Section 5.5, Withdrawal of Subjects](#).

## **4.2 Duration of Subject Participation and Study**

The expected duration of subject participation is up to 36 weeks. The duration of the screening period will be approximately 4 weeks to 10 weeks (allowing for visit windows) and the treatment duration is 24 weeks, with further Safety Follow-up visits at 1 and 2 weeks after last dose (completion or withdrawal).

## **5. SELECTION, WITHDRAWAL OF SUBJECTS AND PERMANENT DISCONTINUATION OF DRUG**

### **5.1 Number of Subjects**

It is anticipated that approximately 20 subjects will be recruited in this study.

### **5.2 Inclusion Criteria**

The following inclusion criteria must be met for each subject:

1. Written informed consent before any study-specific procedures are performed.
2. Male or female subjects with a minimum age of 18 years (or legal age of consent if >18 years) to 75 years of age, inclusive, at the time of consent.
3. Primary FSGS diagnosed by renal biopsy within 6 months prior to the screening visit. Biopsy results over 6 months prior to screening may be permitted following review with the Medical Monitor to confirm eligibility (see [Appendix 3](#)).
4. At initial screening assessment and at last qualifying assessment during screening period prior to baseline, FSGS subjects must have a urine protein creatinine ratio (UPCR) of  $\geq 2.0$  mg/mg. Subjects can be treatment-naïve or receiving steroid treatment (oral or intravenous (IV)) for FSGS. Subjects taking steroids must show signs of improvement in proteinuria, defined as at least a 20% improvement in UPCR from initiation of steroids to the last stability assessment prior to baseline. Subjects who have discontinued steroid treatment due to poor tolerability may be considered for the study. Subjects should also have a serum albumin level of  $\leq 3.2$  g/dL at screening and at the last qualifying assessment prior to baseline; subjects with serum albumin  $> 3.2$  g/dL may be included following review to confirm primary FSGS and after discussion with the Medical Monitor.
5. All subjects should be treated with ACEIs and/or ARBs unless they have documented intolerance or contraindication to these medications. Doses of these agents must be stable for at least 2 weeks prior to baseline, with BP  $\leq 150/90$  mmHg at the baseline visit (Visit 2).
  - a) Subjects with nephrotic edema may be treated with diuretics during the screening period. Volume status should be optimized based on the clinical judgment of the Investigator and the doses of diuretics must be stable in the 2 weeks prior to baseline.
  - b) At the discretion of the Investigator, subjects with hyperlipidemia may be treated with lipid-lowering agents (e.g., statins) in accordance with standard clinical practice. Doses must be stable in the 2 weeks prior to baseline.

6. Stable proteinuria, renal function, and BP during the 2 weeks prior to baseline, as assessed by the Investigator. Changes in UPCR, eGFR, and/or BP during the screening period may be due to treatments administered (e.g., ACEIs and ARBs); and, therefore, may interfere with study assessments or outcomes, or may place the subject at increased risk. All subjects must be discussed with the medical monitor prior to initiation of study treatment.
7. Women of childbearing potential must have a negative serum pregnancy test prior to dispensing study treatment. Two effective forms of contraception must be used simultaneously unless abstinence is the chosen method. Subjects must use effective contraception during the study (see [Section 5.4, Adequate/Effective Contraception](#)).

### 5.3 Exclusion Criteria

1. Subjects unable or unwilling to give written informed consent and/or to comply with study procedures.
2. Clinical or histologic evidence of secondary FSGS.
3. Histologic evidence of collapsing variant FSGS.
4. eGFR as calculated by the CKD-EPI equation of  $\leq 30$  mL/minute/1.73 m^2 at initial screening assessment or  $\leq 45$  mL/minute/1.73 m^2 at last qualifying assessment during screening period prior to baseline.
5. Currently taking or expected to require any of the prohibited medications listed in the protocol (see [Section 7.6.1, Prohibited Medications](#)) at screening or during the study. This includes prior use of cytotoxic or other immunosuppressant treatment for FSGS. Subjects who have discontinued steroid treatment due to lack of response are excluded from the study.
6. Currently requiring renal dialysis (hemodialysis or peritoneal dialysis) or expected to require dialysis during the study period.
7. A previous renal transplant or planned renal transplant during the study.
8. Body mass index  $>40$  kg/m^2 at last stability assessment.
9. Family history of nephrotic syndrome.
10. Any known hypersensitivity or contraindication to cyclosporine, or components of any cyclosporine drug product.
11. Current or medical history of:
  - Congenital or acquired immunodeficiency.

- In the opinion of the Investigator, clinically significant drug or alcohol abuse within 2 years prior to screening.
- Malignancy within 5 years of screening, with the exception of basal and squamous cell carcinomas treated by complete excision. Subjects with cervical dysplasia that is cervical intraepithelial neoplasia 1, but have been treated with conization or loop electrosurgical excision procedure and have had a normal repeat Papanicolaou test are allowed.
- Current or past lymphoproliferative disease or previous total lymphoid irradiation.
- Severe viral infection (e.g., cytomegalovirus, hepatitis B virus, hepatitis C virus) within 3 months of screening, or known HIV infection. Severe viral infection is defined as active disease requiring antiviral therapy.
- Active tuberculosis (TB), or known history of TB/evidence of old TB if not taking prophylaxis with isoniazid.

12. Other clinically significant active medical conditions, such as:

- Severe cardiovascular disease including congestive heart failure, history of cardiac dysrhythmia or congenital long QT syndrome. Subjects with QT interval duration corrected for heart rate using method of Fridericia exceeding 480 msec in the presence of a normal QRS interval (<110 msec) at time of screening are excluded.
- Liver dysfunction: aspartate aminotransferase, alanine aminotransferase, or bilirubin  $\geq 2.5$  times the upper limit of normal at last qualifying assessment during screening period prior to baseline.
- Chronic obstructive pulmonary disease or asthma requiring oral steroids.
- Bone marrow insufficiency: white blood cell count  $< 2,500/\text{mm}^3$ , absolute neutrophil count  $< 1.3 \times 10^3/\mu\text{L}$ , and/or thrombocytopenia (platelet count  $< 50,000/\text{mm}^3$ ) at screening or at last qualifying assessment during screening period prior to baseline.
- Current infection requiring IV antibiotics.

13. Any overlapping autoimmune condition for which the condition or the treatment of the condition may affect the study assessments or outcomes (e.g., any condition for which additional immunosuppression, including systemic corticosteroids, and/or cytotoxic therapy is indicated). Overlapping conditions for which the condition or treatment is not expected to affect assessments or outcomes are not excluded.

14. No vaccines using live organisms, viral or bacterial, are allowed during screening and while taking the study treatment.
15. Other major physical or psychiatric illness or major traumatic injury within 6 months prior to screening that may affect study conduct or interfere with study assessments or outcome.
16. Any other medical condition which, in the Investigator's judgment, may be associated with increased risk to the subject or may interfere with study assessments or outcomes.
17. Subjects who are pregnant, breast feeding or, if of childbearing potential, not using adequate contraceptive precautions.
18. Participation in another interventional clinical study within 4 weeks prior to screening and/or receipt of investigational drugs within 4 weeks or 5 half-lives of the drug (whichever is longer) prior to screening.
19. Subjects treated in a previous voclosporin clinical study.

#### **5.4 Adequate/Effective Contraception**

Women of childbearing potential must have a negative serum pregnancy test during screening and a negative urine pregnancy test at baseline. Two effective forms of contraception must be used simultaneously unless abstinence is the chosen method. Effective contraception must be used before beginning study treatment, during study dosing, and for 6 weeks following discontinuation of study treatment, even when there has been a history of infertility, unless due to surgical sterilization. Women not of childbearing potential are defined as women without menses for at least 12 consecutive months or surgically sterilized.

Sexually active, reproductively competent men are required to use condoms during treatment and for at least 6 weeks after cessation of study treatment. In addition, female partners of male subjects are recommended to use an effective contraception during their partner's treatment and for at least 6 weeks after the last dose of study treatment. Male subjects are to refrain from making sperm donations during treatment and for at least 6 weeks after cessation of study treatment.

An effective and medically acceptable method of birth control means the chance of pregnancy, when using that type of birth control, is less than 1% per year if used correctly. These birth control methods (i.e., reliable forms of contraception) include birth control pills (combined oral contraceptives), hormone implants, hormone shots, and some intrauterine contraceptive devices.

Barrier methods (e.g., condoms, diaphragm, or cervical cap/sponge) when used alone are not considered highly effective.

Although abstinence, when adhered to, is an effective method of birth control, other additional effective contraception methods should be used where there is any doubt. The method of contraception needs to be discussed with the Investigator and documented throughout the study period in order to confirm the method used is considered effective.

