- 4 BP, pulse, temperature, weight, and height. Height included at initial screening assessment only. At stability assessments, BP only will be included.
- 5 In the event that a subject is noted to have a QTcF value exceeding 500 msec, or an increase of  $>60$  msec from baseline, the ECG should be repeated within 24 hours. Further details provided in the study protocol.
- 6 Laboratory assessments will be performed according to the schedule in the study protocol. Subjects must be fasting for at least 8-12 hours at Baseline and at end of study/early termination visit.
- 7 Pharmacokinetic assessments will be done at Weeks 4 and 24. PK samples will be drawn prior to study treatment dosing (trough sample), and at 1, 2 and 4 hours post-dose. In the event a subject experiences an SAE or requires a dose modification or is withdrawn from treatment, a voclosporin sample should be taken, with a trough sample preferred.
- 8 The UPCR will be calculated both from the FMV and from standard urinalysis results. If the FMV is for some reason not available, then standard urinalysis from a 24-hour urine collection may be substituted as an exception but only after agreement is reached with the Medical Monitor.
- 9 24-hour urine collection should begin 2 days prior to the scheduled study visit in order not to coincide with the FMV sampling due on the day of the study visit.
- 10 Patient Reported Outcome Measurement Information system (PROMIS) and Kidney Disease Quality of Life-Short Form (KDQOL-SFTM).
- 11 Serum pregnancy test to be evaluated at central laboratory at Screening and Week 24; urine pregnancy test will be performed locally at all other visits as applicable.
- 12 If screening visit occurs on the same day as informed consent, any findings are to be recorded as Medical History. Any change since the date of signed consent and/or during the screening period would be considered an AE.
- 13 Subjects in Cohort 1, will be contacted by telephone at the end of Week 1 as a reminder to increase their dose to 2 capsules (15.8 mg) BID for 1 week, starting at Week 2. Subjects will be contacted again by telephone at the end of Week 2 as a reminder to increase their dose to 3 capsules (23.7 mg) BID, starting at Week 3, for the remainder of the treatment period. Subjects in Cohort 2, will also be contacted at the end of each week (as required) up to Week 4, as a reminder to increase their dose to the maximum selected for Cohort 2.
- 14 Compliance only.

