Pregnancy Test	For females of childbearing potential.	Serum pregnancy test to be evaluated at central laboratory at Screening, and Week 24; urine pregnancy test will be performed locally at all other applicable visits.
Serology	Cytomegalovirus Hepatitis A, B, and C Hepatitis B surface antigen (HBsAg)	Screening (including stability assessments)
Special Tests	Estimated glomerular filtration rate (eGFR)	All
Biomarkers	Urine nephrin Urine synaptopodin Serum TGF- $\beta$	Day 1, Week 4 and Week 24

Notes: FMV = First morning void; HDL = High-density lipoprotein; LDL = Low-density lipoprotein; UPCR = Urine protein creatinine ratio.

The total amount of blood that will be collected during the study from an individual subject is approximately 200 mL over 34 weeks.

For details on whether laboratory abnormalities should be reported as AEs and on the follow-up required in such cases, see [Section 10.2.4, Clinical Laboratory Evaluations](#).

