### **9.2.1 Screening Visit and Stability Assessment Procedures**

The duration of the screening period will be approximately 4 weeks to 10 weeks (allowing for visit windows) and will consist of an initial screening assessment and 2 to 4 stability assessments to ensure that subjects meet eligibility criteria.

The initial screening assessment will include provision of informed consent; complete physical examination; medical history (including FSGS history); vital signs measurements, including weight and height; 12-lead ECG; blood and urine sample collection for central laboratory assessments, urinalysis, and urine microscopy; FMV urine collection (for determination of UPCR); a serum pregnancy test (for women of childbearing potential); and review of prior and concomitant medications and entry criteria. Following these assessments and if clinically indicated, subjects receiving steroids may start reducing their steroid dose as described in the corticosteroid dosing guidelines (see [Section 7.1.2.2, Corticosteroids](#)). Any AEs which occur after informed consent will be recorded.

Stability assessments will occur at 14-day intervals ( $\pm 3$  days) with the first assessment approximately 2 weeks after the initial screening assessment visit. Stability assessments 1 and 2 are mandatory; assessments 3 and 4 are optional if additional time is required for the subject's clinical status to stabilize. These stability assessment visits will include BP determination; blood sample collection for central laboratory assessments; FMV urine collection (for determination of UPCR); a serum pregnancy test (for women of childbearing potential); review of any AEs; and review of concomitant medications and entry criteria.

These renal disease stability assessments will be evaluated to ensure eligibility with respect to entry criteria for UPCR and eGFR.

Note that the laboratory assessments and FMV results of the last stability assessment will be used as the qualifying values for eligibility.

FMV urine samples (for determination of UPCR) will be collected at all visits during the screening period and must be returned and the results evaluated prior to Baseline/Day 1. If the FMV is for some reason not available at Day 1, Week 12 or Week 24, standard urinalysis from a 24-hour urine collection may be substituted as an exception but only after agreement is reached with the Medical Monitor.

Blood samples will be drawn according to [Table 1](#).

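### Section 5.4 treats 12 months without menses from any cause as proof of no childbearing potential, so some premenopausal women fall outside the pregnancy tests tied to that status

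*Combined protocol and SAP*

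**What the plan says.** Section 5.4 (Adequate/Effective Contraception) gives the protocol's only definition of who is not of childbearing potential: "Women not of childbearing potential are defined as women without menses for at least 12 consecutive months or surgically sterilized". Among the methods it regards as reliable, the section names "hormone implants, hormone shots, and some intrauterine contraceptive devices".

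Several requirements then depend on childbearing status:

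- Section 5.2, inclusion 7: "Women of childbearing potential must have a negative serum pregnancy test prior to dispensing study treatment".
- Section 5.4: "Women of childbearing potential must have a negative serum pregnancy test during screening and a negative urine pregnancy test at baseline".
- Section 5.3, exclusion 17: "Subjects who are pregnant, breast feeding or, if of childbearing potential, not using adequate contraceptive precautions".
- Section 9.1.1, Table 1, pregnancy test row: "For females of childbearing potential".
- Section 9.2.1 ties the serum tests at screening and at the stability assessments to the same group. Section 9.2.2 does so for the serum test in screening and the urine test before dispensing on Day 1.
- Schedule of Events, footnote 11, after naming the serum tests at Screening and Week 24: "urine pregnancy test will be performed locally at all other visits as applicable".

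Inclusion 2 admits adults from 18 to 75 years.

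**The concern.** Twelve months without menses is a reasonable marker of menopause only when nothing else explains it. The definition does not ask why menses stopped. It therefore places a young woman whose periods stopped because of a contraceptive or an illness in the same class as a postmenopausal or sterilised woman. That these things can stop menses is general knowledge, not something the documents state. The point needs only the fact that the text ignores cause.

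What is at stake is detection of pregnancy before and during dosing. The protocol treats pregnancy as a bar to entry (exclusion 17). Under Section 10.3.3, a positive test means withdrawal from study treatment and immediate contact with the Medical Monitor. Section 9.1.2 describes the study drug as an immunosuppressant. A definition that drops the required test for a woman who could conceive works against these provisions.

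**Working it through.** No statistical calculation applies. The check is a reading of every place where childbearing status decides what is required, followed by a count of scheduled tests.

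**Step 1: Is the amenorrhoea limb qualified anywhere?** Section 5.4 adds no menopause, age, hormone or cause condition. Sections 5.2, 5.3, 9.1.1, 9.2.1 to 9.2.3, 10.3.3 and the Schedule of Events use the status or the tests but supply no condition either. With entry from age 18, premenopausal women are eligible, so the unqualified wording can reach them.

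**Step 2: Which requirements clearly depend on the status?** The first sentence of inclusion 7, the contraception part of exclusion 17, the screening and baseline tests in Section 5.4, the pregnancy row of Table 1, the screening and stability tests in Section 9.2.1, and the serum and Day 1 urine requirement in Section 9.2.2. A woman classed as not of childbearing potential is outside all of these.

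**Step 3: Which texts do not clearly depend on it?**

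| Place | Scope as written |
|---|---|
| Inclusion 7, last sentence | Contraception during the study is required of subjects, with no limit to childbearing potential; it refers the reader to Section 5.4 |
| Section 5.4, sentence before the definition | Contraception before, during and for 6 weeks after treatment; a history of infertility does not lift it, and only surgical sterilisation does |
| Exclusion 17, pregnancy and breast-feeding | Applies whatever the childbearing status |
| Section 9.2.2, visit list | Day 1 urine test, no qualifier |
| Section 9.2.3, end-of-study list | Serum test, no qualifier |

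The second row sits beside the definition and differs from it. One sentence excepts surgical sterilisation alone; the next also sets apart women with 12 months of amenorrhoea. The text does not say which controls the contraception duty.

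**Step 4: Size for one affected woman.** The Schedule of Events marks pregnancy tests at the screening visit (1), at the stability assessments (2 mandatory, up to 4) and at Visits 2 to 8 (7 visits). None is marked at Visits 9 or 10.

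- Scheduled occasions: 1 + 2 + 7 = 10 at least, and 1 + 4 + 7 = 12 at most.
- If Table 1's limit governs, none of these 10 to 12 is required for her.
- If the unqualified lists in Sections 9.2.2 and 9.2.3 govern, Day 1 and Week 24 remain, so 10 − 2 = 8 to 12 − 2 = 10 are not required.

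**Step 5: How many women?** The documents give neither the expected number of premenopausal women among the approximately 20 subjects nor a rate of amenorrhoea. No count can be derived, and zero is possible.

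**The case against.** The strongest reply is that the practical consequence is small. A woman whose periods stopped because of an implant, an injection or an intrauterine device is, while she continues it, using a method of the kind Section 5.4 lists. The contraception sentences in inclusion 7 and Section 5.4 are not expressly limited to women of childbearing potential. Two visit lists call for a pregnancy test without qualification. A known pregnancy excludes any subject, every subject is discussed with the Medical Monitor before treatment, and a female subject must tell the investigator at once if she becomes pregnant. An investigator may always test anyway. The study is descriptive, and the issue changes no endpoint or analysis set.

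Most of this stands, and it limits the point. A reader might infer that such a woman is released from contraception altogether, or that she may stop the method that caused the amenorrhoea. The documents do not support that: the sentence before the definition excepts only surgical sterilisation, and inclusion 7 speaks of subjects generally. A reader might also infer that entry testing and on-study detection are wholly removed. That too goes beyond the text, given the unqualified Day 1 and Week 24 lists and the pregnancy part of exclusion 17.

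What the reply does not remove is the gap in required testing. Exclusion of a known pregnancy and self-report are not tests. Table 1 limits the tests that the two lists leave open. A woman with amenorrhoea from illness need not be using any method. Nothing obliges a site to look past the definition.

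**Conclusion.** The definition is a stated rule that misclassifies some premenopausal women, and it should be corrected. For an affected woman, 8 to 12 scheduled pregnancy tests are not required, depending on whether Table 1 or the unqualified lists govern and on whether 2 or 4 stability assessments take place. The contraception part of exclusion 17 does not apply to her. Her position under the other contraception sentences is unclear.

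The two adjacent sentences in Section 5.4 are in tension. A reader might call this a flat contradiction in which the permissive sentence wins. The text does not establish that: infertility and amenorrhoea are different things, and the sentences can be read together, though with different exceptions. They need reconciling.

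A reader might also want a figure for the number affected. Any such figure would rest on rates of contraceptive use and amenorrhoea that the documents do not contain, so none is given. The conclusion assumes a literal reading by sites and that at least one eligible premenopausal woman could have 12 months of amenorrhoea. It concerns subject safety only and has no bearing on the efficacy estimates.

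**What to change.** In Section 5.4, reconcile the definition with the sentence before it, and limit the amenorrhoea limb to postmenopausal women. Suggested sense: a woman is not of childbearing potential if she is surgically sterilised, or if she is postmenopausal, meaning at least 12 consecutive months without menses that are not explained by another cause such as contraception or illness. All other women then fall under inclusion 7, exclusion 17 and the pregnancy tests already scheduled from screening through Week 24 (Visit 8). The contraception sentence should name the same exceptions as the definition. While the text is open, the lists in Sections 9.2.2 and 9.2.3 could carry the same qualifier as Table 1, so that all places agree.

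The cost is a short edit to one section, with the ethics approval that Section 17.1 requires for an amendment, and a few more tests: at most the 10 to 12 already in the schedule for each woman reclassified. No visit or new procedure is added.
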